3.2 Exclusion Criteria

- Patients with clinically significant illnesses which would compromise participation in the study, including, but not limited to: active or uncontrolled infection, uncontrolled diabetes, uncontrolled hypertension, symptomatic congestive heart failure, unstable

angina pectoris, myocardial infarction within the past 6 months, uncontrolled cardiac arrhythmia; or psychiatric illness/social situations that would limit compliance with study requirements.

- Patients may not be receiving any medication that may markedly affect renal function (e.g., vancomycin, amphotericin, ibuprofen, pentamidine).
- Patients who are unable to swallow tablets.
- Mean QTc >500 msec (with Bazett's correction) in screening electrocardiogram or history of familial long QT syndrome.
- Greater than +1 proteinuria on two consecutive dipsticks taken no less than 1 week apart.
- Pregnant women are excluded from this study because AZD2171 is a VEGF inhibitor with known abortifacient effects. Because there is an unknown but potential risk for adverse events in nursing infants secondary to treatment of the mother with AZD2171, breastfeeding should be discontinued if the mother is treated with AZD2171.
- HIV-positive patients on combination antiretroviral therapy are ineligible because of the potential for PK interactions with AZD2171.
- Adult patients with hypertension not controlled by medical therapy (hypertension defined as systolic blood pressure >150 mmHg or diastolic pressure > 90 mmHg despite optimal medical management). Pediatric patients must have BP WNL for age. NOTE: blood pressure within the upper limit of normal is defined as: blood pressure \leq the 95th percentile for age, height, and gender (Appendix I), and measured as described in Section 3.3.1, and not be receiving medication for treatment of hypertension.

3.3 Research Eligibility Evaluation

3.3.1 Clinical Evaluations

- A complete history and physical examination (including blood pressure, pulse, respiratory rate, and temperature) will be completed within 72 hours prior to the subject starting study drug. Patients <16 years old will have height and weight measured 3 consecutive times at baseline, and BSA calculated for dosing. Clinical evaluation will also include determination of performance status.
 - **Baseline blood pressure** in the pediatric patient is defined as the blood pressure obtained at the examination used for study enrollment. This baseline BP should be obtained as follows:
 - 1) Obtain 3 serial blood pressures from the same extremity with the patient in the same position that are separated by at least 5 minutes. Avoid using the lower extremity if possible.
 - 2) Average the systolic blood pressure from the 2nd and 3rd measurements.
 - 3) Average the diastolic blood pressure from the 2nd and 3rd measurements.
 - 4) The baseline BP is the average of the systolic over the average of the diastolic measurements.
- EKG will be done for determination of QTc within 72 hours prior to starting study drug.
- Pediatric patients: echocardiogram within 2 weeks of enrollment on study.
- Diagnostic imaging studies must be performed within 30 days prior to enrolling on study.

- PET scans will be done at baseline and, if clinically indicated, at restaging.
- After determining eligibility, pediatric patients will undergo lower extremity scanogram and unilateral knee MRI (if applicable) according to Appendix K.

3.3.2 *Laboratory Evaluations*

Baseline laboratory tests should be performed within 72 hours prior to receiving the study agents unless stated otherwise.

- Hematological profile: CBC with differential and platelet count
- Biochemical profile: electrolytes, BUN, creatinine, glucose, AST, ALT, bilirubin, calcium, phosphorous, albumin, magnesium, alkaline phosphatase, LDH
- TSH and T4
- Urinalysis
- Urine pregnancy test in women of childbearing potential

3.3.3 *Pathology Review*

A block or stained slides of primary tissue from the time of diagnosis will be required from each study subject to confirm diagnosis. Tissue blocks from a known recurrence will be accepted if the original tumor samples are unavailable. Diagnosis of ASPS must be confirmed by the Laboratory of Pathology at the Clinical Center, NIH, prior to patient enrollment.

3.4 Patient Registration

Authorized staff must register an eligible candidate with the NCI Central Registration Office (CRO) within 24 hours of signing consent. A registration Eligibility Checklist from the Web site (<http://home.ccr.cancer.gov/intra/eligibility/welcome.htm>) must be completed and sent via encrypted email to: NCI Central Registration Office (HOIS) ([contact]). After confirmation of eligibility at Central Registration Office, CRO staff will call pharmacy to advise them of the acceptance of the patient on the protocol prior to the release of any investigational agents. Verification of Registration will be forwarded electronically via e-mail.

3.5 Off Protocol Therapy and Off-Study Procedure

Authorized staff must notify the CRO when a patient is taken off protocol therapy and when a patient is taken off-study. The Participant Status Updates Form from the Web site (<http://home.ccr.cancer.gov/intra/eligibility/welcome.htm>) main page must be completed and sent via encrypted email to: NCI Central Registration Office (HOIS) ([contact]).

4 Treatment Plan

This is a Phase II trial of AZD2171 in patients with ASPS.

4.1 AZD2171 Administration

The adult cohort met study objectives and was closed to accrual with Amendment K, 02/01/13.

Adult patients will receive 30 mg AZD 2171 tablets orally once a day in a 28-day cycle. AZD2171 will be available as 15 and 20 mg tablets. The dose of 30 mg daily has been shown to be safe in multiple Phase I and II trials of AZD2171 as a single agent. In the early phase trial that showed activity of AZD2171 in patients with metastatic ASPS, the initial dose of AZD2171 was 45 mg po each day. However, most patients required a dose reduction to 30 mg po each day due to associated toxicities. Dose modifications are outlined in Section 5.

Pediatric patients will receive 12 mg/m²/dose (equivalent to 20 mg per dose based on a BSA of 1.8 m²) according to the Pediatric Dosing Nomogram (Appendix H). Dose adjustments may be made based on changes in height and weight in pediatric patients at the time of restaging evaluations. If the pediatric patient is unable to maintain the study diary independently, the following instructions will also be presented to the parent(s).

No investigational or commercial agents or therapies other than those described below may be administered with the intent to treat the patient's malignancy. Patients will take AZD2171 on an empty stomach (either 1 hour before or 2 hours after meals). The drug will be administered once daily at approximately the same time each day. Tablets must be swallowed whole and not crushed. A new cycle may begin 1 day earlier or 1 day later than it would otherwise be scheduled based on the 28-day cycle, to allow for flexibility for days the clinic is closed and other unexpected events.

Note: For patient convenience, 2 cycles' worth of drug may be dispensed at a time to patients who have been on study for over a year and are tolerating treatment well. For patients who have been on study for over 18 cycles, 3 cycles' worth of drug may be dispensed; for patients who have been on study for over 36 cycles, 4 cycles' worth of drug may be dispensed; for patients who have been on study for over 60 cycles, 6 cycles' worth of drug may be dispensed.

Patients will be provided with a Study Diary (Appendix C), instructed in its use, and asked to bring it with them to each appointment. A new copy of the Study Diary will be given to patients whose dose is reduced due to adverse events. After cycle 2, a cycle will be considered completed if 90% of the prescribed doses are administered.

Blood pressure will be monitored every 2 weeks by a health care provider during the first 2 cycles, then at the start of each subsequent cycle (unless patients have experienced elevated blood pressure requiring drug therapy, in which case, the frequency of monitoring blood pressure will be determined by the study doctors and the patient instructed appropriately). Patients will be instructed to check their blood pressure at home more frequently.

CT scans will be performed at baseline and repeat imaging scans will be performed every 2 cycles during the first 18 cycles. After 18 cycles, CT scans will be performed every 3 cycles; after 36 cycles, every 4 cycles; and after 60 cycles, every 6 cycles. Patients may be

scanned earlier if clinically indicated. PET scans will be done at baseline and, if clinically indicated, at restaging.

Labs (CBC with differential, serum chemistries) will be performed every week for the first cycle, then every 2 weeks for cycles 2 and 3, and then at the start of each subsequent cycle. Physical assessment will be performed once per cycle for patients in cycle 2 onwards. For patients who have been on study for over a year up to 18 cycles (and are tolerating treatment well), physical exam/labs will only be performed once every 2 cycles/8 weeks. For patients who have been on study for more than 18 cycles up to 36 cycles, physical exam/labs will only be performed once every 3 cycles/12 weeks. For patients on study more than 36 cycles up to 60 cycles, physical exam/labs will be performed every 4 cycles/16 weeks. Patients on study more than 60 cycles will have physical exam/labs performed every 3 cycles/12 weeks, but every other exam/set of labs (when a CT scan is not required) may be performed by the patient's local physician. More frequent labs and assessment can be performed as clinically indicated. EKGs will be performed at baseline and as clinically indicated. ECHO/MUGA will be performed in adults as clinically indicated, and in all pediatric patients at baseline and serially thereafter (see Section 10).

Plain radiographs of tibial growth plates will be performed in all patients <16 years of age at study enrollment. Plain radiographs will be 2-view pictures: AP and lateral. Plain radiographs do not have to be performed in patients \geq 18-years-old. In patients with open growth plates follow-up plain radiographs of the tibial growth plates will be performed as clinically indicated. Patients with evidence of open growth plates on plain radiographs will also have a growth plate (knee) MRI to further evaluate physeal pathology at baseline, and then after cycles 2, 4, 8, 12, and every 4th cycle thereafter.

Optional tumor biopsies will be collected prior to starting treatment on study (baseline) and then after completion of 3 -5 days of therapy (cycle 1, D3-D5) in adults only (the adult cohort has met study objectives and is closed to accrual. No biopsies will be collected on this protocol). A third optional biopsy after completion of at least 4 weeks of therapy (between C1D28 and C2D7) will be collected. Based on initial gene analysis results, the timing of the biopsies may change. However, the total number of biopsies per patient will not change.

Research biopsies will be performed only if minimal risk to the patient is estimated (Section 9.1.2). Determination of a disease site amenable to biopsy will be determined on an individual case basis after discussion with an interventional radiologist.

- All biopsies will be optional
- All biopsies will be by percutaneous approach
- No biopsy by an invasive (endoscopic, laparoscopic, or surgical) procedure will be performed.
- No visceral organ (ex. liver) biopsy will be performed, with the exception of lung.
- No core biopsies of lung lesions.
- Only fine needle aspiration (FNA) will be performed. FNA of lung lesions has been demonstrated to be safe. In a recent study, pneumothorax complication rate was < 10%, with only one patient out of 26 requiring a chest tube placement [36].

5 Dosing Delays/Modifications

5.1 Dose Modifications

Dose will be modified for grade 3 or greater non-hematologic toxicity (except electrolyte abnormalities unless these are not correctable within 48 hours) and/or grade 4 hematologic (except lymphopenia, anemia) toxicity. A maximum of 2 dose reductions will be allowed before the patient is taken off treatment. Patients who require a dose-reduction will not have the dose re-escalated. No more than 2 dose reductions will be allowed.

If administration of AZD2171 is interrupted for any reason, counting of the cycle days continues (i.e., if a patient stops drug on Day 15 and resumes 2 days later, they will be considered on Day 17).

5.1.1 Dose Modifications in Adults

All adult patients will be started on the initial dose of 30 mg po once per day for 28 days, in 28-day cycles.

Dose Modification table for adults:

Dose Level	Dose (mg/day)
1	30
-1	20
-2	15

Patients who tolerate the 30-mg dose for 2 cycles may, at the PI's discretion, have their dose increased to 45 mg [this was the initial dose used in the early-phase trial that showed activity in patients with ASPS, even though most patients required a dose reduction to 30 mg].

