In the Phase I study in patients with solid tumors and metastatic liver disease (Study 2171IL/0001; N = 83), there were 2 confirmed partial responses and 22 patients with stable disease. Minor responses were observed in 2 patients with breast cancer and 1 patient each for colorectal, lung, head and neck, liver, and skin/soft tissue tumor types. Reductions in tumor blood flow and permeability were detected by DCE-MRI, and there were time- and dose-dependent decreases in VEGFR-2 levels. Data from this trial suggest AZD2171 is biologically active at doses of 20 mg and higher.

Although 45 mg was the initial recommended Phase II dose based on results from Study 2171IL/0001, subsequent studies have indicated that many patients are not able to tolerate this dose and require a dose reduction ([Table 1](#)) [21]. For example, the starting dose was reduced to 30 mg in two monotherapy Phase II trials in ovarian cancer due to toxicities observed at the 45-mg dose level [22, 23]. In one of these trials, 28 patients received AZD2171, and Grade ≥ 3 AEs included hypertension (5 patients at 45 mg, 8 patients at

30 mg), fatigue (5 patients), diarrhea (3 patients), vomiting (2 patients), hyponatremia (2 patients), oral cavity pain (2 patients), and nausea, constipation, abdominal pain, headache, and hypothyroidism (all 1 patient each); Grade 4 toxicities included CNS hemorrhage (1 patient at 45 mg), lipase (1 patient) and hypertriglyceridemia (1 patient) [22]. In the other trial, hypertension (33%) and fatigue (20%) were the most frequent Grade ≥ 3 AEs [23]. Similarly, in a Phase II study of AZD2171 in recurrent small cell lung cancer, 7 of the first 12 patients enrolled were unable to complete the first cycle at 45 mg due to AEs, and the starting dose was subsequently reduced to 30 mg [24]. Salient Grade 3 toxicities were fatigue (4 patients), proteinuria (2 patients), diarrhea, skin rash, transaminitis, muscle weakness, and hypertension (all 1 patient each). Two patients had Grade 4 fatigue.

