In summary, a higher incidence of toxicities has been observed in several studies at 45 mg, and subsequently 30 mg has been widely used as a single-agent Phase II dose. In a randomized study evaluating both the 30 and 45 mg doses of AZD2171 with or without antihypertension prophylaxis in patients with advanced solid tumors, the overall response rate was similar across treatment groups with evidence of antitumor activity at both the 30-mg and 40-mg dose levels (N = 125; Investigator's Brochure). Ryan et al. reported that AZD2171 doses as low as 20 mg daily in patients with advanced prostate cancer resulted in plasma concentrations above the concentration required to inhibit endothelial cell growth [25].

In reference to this particular protocol and ASPS, the starting dose of 30 mg was chosen after review of the safety data from the Phase I and II trials sponsored by Astra Zeneca at the Royal Marsden Hospital, London, UK and the Christie Hospital, Manchester, UK. The clinical efficacy data which forms the basis for conducting this study (Section 2.2.4) is from the trials conducted by the group of investigators at these institutions. Patients with ASPS were unable to tolerate 45 mg for more than 1 to 2 cycles of therapy and then required dose modification for toxicity, particularly liver function test abnormalities. The starting dose was subsequently decreased to 30 mg; this dose was more tolerable with a manageable toxicity profile and for much longer durations. These observations were corroborated by Grade 3 elevation in transaminases within the first 2 weeks of a patient receiving AZD2171 by special exemption protocol at our institution, which resulted in dose reduction to 30 mg.

Table 1: Summary of Pertinent Clinical Trials With AZD2171 [21]

Study	Clinical phase	Cancer type	Dose(s) used	Significant toxicities	Efficacy
Drevs et al. (2007)	Phase I	Solid tumors	RP2D = 45 mg once-daily	21/83 DLTs including hypertension (most commonly), fatigue and nausea	2/83 partial responses 22/83 stable disease
Laurie et al. (2008)	Phase I	Lung	RP2D = 30 mg (with carboplatin + paclitaxel)	Grade III-IV: hypertension (35%), fatigue (60%), anorexia (35%), diarrhea (30%), mucositis (20%)	9/20 partial responses 11/20 stable disease

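### Adults raised to 45 mg get at most 3 scheduled liver test sets in their first two cycles at that dose, against 6 when starting 30 mg, because the schedule runs on study cycle number and is not restarted.

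*Combined protocol and SAP*

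**What the plan says.** Section 5.1.1 starts every adult at 30 mg daily. After two tolerated cycles the PI may let the patient "have their dose increased to 45 mg [this was the initial dose used in the early-phase trial". The same sentence admits that most patients in that trial had to come down to 30 mg. It gives an earliest time for the increase but no latest time.

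Section 4.1 schedules labs "every week for the first cycle, then every 2 weeks for cycles 2 and 3, and then at the start of each subsequent cycle". For patients on study over a year, up to 18 cycles and doing well, "physical exam/labs will only be performed once every 2 cycles/8 weeks". From there to 36 cycles, "physical exam/labs will only be performed once every 3 cycles/12 weeks". The interval is 4 cycles up to cycle 60 and 3 cycles after that. Footnote m of the Section 10 calendar repeats this schedule and lets start-of-cycle labs be drawn up to 8 days early. Footnote d puts AST and ALT in the chemistry set.

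Clinic blood pressure is two-weekly for two cycles and then once per cycle (précis, Sections 4.1 and 5.2.3, footnote b, Appendix E). For patients whose blood pressure has needed drug treatment, the study doctors set the frequency. None of these places restarts a schedule at a dose increase.

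On 45 mg, Section 2.2.3 states: "Patients with ASPS were unable to tolerate 45 mg for more than 1 to 2 cycles of therapy", after which the dose was modified for toxicity, "particularly liver function test abnormalities". It supports this with a "Grade 3 elevation in transaminases within the first 2 weeks of a patient receiving AZD2171 by special exemption protocol", after which that patient was reduced to 30 mg. In a small cell lung cancer trial, "7 of the first 12 patients enrolled were unable to complete the first cycle at 45 mg due to AEs".

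**The concern.** Monitoring is densest at the dose the protocol regards as tolerable and thinnest at the dose it describes as poorly tolerated. A transaminase rise can be silent, so a scheduled draw is the only step that finds it without a prompt. Under Section 5.2.2 a grade 3 rise calls for holding the drug. If no draw falls due, dosing at 45 mg can continue through such a rise until someone chooses to test. After the first year the next scheduled draw may be 7 weeks or more away. Section 4.1 also allows several cycles of drug to be dispensed at once by then, which reduces chance contact with the clinic.

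**Working it through.** The protocol states no figure for this point, so there is nothing to reproduce. The check is a direct count from Section 4.1 and the Section 10 calendar with footnotes b, d and m.

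Convention: d is the number of days since the first dose at the level. Count scheduled draws with 0 < d ≤ 56, which is two 28-day cycles. Assume the increase falls on day 1 of a cycle.

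| Dose and time of start | Scheduled draws (d) | Sets by day 56 | First scheduled AST/ALT |
|---|---|---|---|
| 30 mg, study start | 7, 14, 21, 28, 42, 56 | 6 | day 7 |
| 45 mg, cycle 3 | 14, 28, 56 | 3 | day 14 |
| 45 mg, cycle 4 or soon after | 28, 56 | 2 | days 20–28 |
| 45 mg, after a year to 18 cycles | 28 or 56 | 1 | days 48–56* |
| 45 mg, 19–36 cycles | every 84 days | 0 or 1 | days 76–84* |
| 45 mg, 37–60 cycles | every 112 days | 0 or 1 | days 104–112* |
| 45 mg, over 60 cycles | every 84 days | 0 or 1 | days 76–84* |

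*If the increase is made at a lab visit.

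The lower ends of the ranges come from the 8-day window: 28 − 8 = 20, 56 − 8 = 48, 84 − 8 = 76, 112 − 8 = 104.

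Sensitivity to the convention:
- Counting the first-day draw and leaving out day 56 still gives 6 against 3.
- Leaving out both gives 5 against 2.
- Trying every possible day of increase from cycle 3 day 1 onward, mid-cycle days included, gives a maximum of 3.

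Clinic blood pressure, for patients not already on antihypertensives: 30 mg start at d = 14, 28, 42, 56, so 4 readings; 45 mg from cycle 3 or later at d = 28, 56, so 2.

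Extra lab sets needed to match the starting schedule: 6 − 3 = 3, 6 − 2 = 4, 6 − 1 = 5, 6 − 0 = 6.

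Early intolerance of 45 mg in the lung cancer trial: 7/12 = 58%, exact (Clopper-Pearson) 95% CI 28% to 85%. This covers all adverse events. The same paragraph lists grade 3 transaminitis in one patient, so the 58% is not a liver figure.

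**The case against.** The strongest argument is reach. Adult accrual closed with Amendment K in February 2013. Section 2.4 reports one adult still on drug, after 133 cycles, and nothing says any adult was ever raised to 45 mg. This stands, and it is why the point is minor.

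Next, the natural time to escalate is cycle 3, when labs are still two-weekly and the first draw comes at day 14. That is fair, and the longest waits are hypothetical. But Section 5.1.1 sets no latest time, and even at cycle 3 the count is half that at the 30 mg start. The thinner labs between one year and 18 cycles are limited to patients tolerating treatment well, but a patient chosen for a dose increase would normally meet that condition.

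The evidence is also thin. The early grade 3 rise is one patient on another protocol, whose starting dose is not given. The other patients had not first tolerated 30 mg for two cycles, so the risk after a tolerated lead-in may be lower. Problems after 1 to 2 cycles would fall near days 28 to 56, when draws do occur for increases at cycle 3 or 4. These points weaken any estimate of how often harm would occur. They do not supply a reason to test less at the higher dose.

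Last, there are safeguards: extra tests as clinically indicated, at least weekly labs once a toxicity is known (5.2.2), two-weekly data review and weekly team meetings (12.2), continuing adverse event evaluation, and morning and evening blood pressure in the diary (Appendix C). The PI who approves the increase can also order labs. All this makes an unwatched increase less likely. None of it requires an AST/ALT draw after the increase, and reviewing data cannot reveal a test that was not taken.

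**Conclusion.** The concern holds, as a minor safety weakness in a stated rule. An adult raised to 45 mg has 3 or fewer scheduled liver test sets in the first 56 days at that dose, against 6 at the 30 mg start. The first scheduled test moves from day 7 to day 14 at best, to days 20–28 for an increase at cycle 4, and to days 76–84 for a patient past 60 cycles who is raised at a lab visit. The one remaining adult is in that last group.

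The counts refer to scheduled draws only, with the increase on day 1 of a 28-day cycle; a mid-cycle increase shortens the first wait. How often a rise would be missed cannot be estimated from the documents. No endpoint or analysis is affected.

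**What to change.** Add one sentence to Section 5.1.1: from the first 45 mg dose, chemistries including AST and ALT are drawn weekly for one cycle and every 2 weeks for the next, and clinic blood pressure is taken every 2 weeks for two cycles, whatever the study cycle number. Urine protein can be checked at the same visits. Cross-refer to the sentence in six places so that every copy of the schedule agrees: the précis, Sections 4.1 and 5.2.3, calendar footnotes b and m, and Appendix E.

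The cost per escalated patient over 8 weeks is 3 to 5 extra routine lab sets (up to 6 if raised after 18 cycles) and 2 extra clinic blood pressure readings. No new type of test is needed.
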